11.2.3. All Events

Regardless of whether the patient continues on Fampyra or not, any AE as defined in Section 11.2.2 experienced by a patient between the time of first dose of Fampyra and Study Completion or Early Study Discontinuation Visit is to be recorded on the CRF, regardless of the severity of the event or its relationship to study treatment.

All events must be assessed to determine the following:

- whether the event meets the criteria for an SAE as defined in Section 11.1.2
- the relationship of the event to Fampyra treatment as defined in Section 11.3.1
- the outcome of the event

CONFIDENTIAL

The information contained herein may not be used, disclosed, or published without the written consent of Biogen Idec MA Inc.

11.2.4. Reporting of Serious Adverse Events

In order to adhere to all applicable laws and regulations for reporting an SAE, the study site must formally notify Quintiles as soon as possible, within 24 hours of the study site staff becoming aware of the SAE. It is the Investigator's responsibility to ensure that the SAE reporting information and procedures are used and followed appropriately.

Reporting Information for SAEs

Any Serious Event that occurs between the time of first dose of Fampyra and Study Completion or Early Study Discontinuation Visit must be reported to Quintiles as soon as possible, within 24 hours of the study site staff becoming aware of the event.

A report ***must be submitted*** to Quintiles regardless of the following:

- the severity of the SAE; and
- the relationship of the event to Fampyra treatment.

To report initial or follow-up information on a Serious Event, the SAE form must be faxed to the local Quintiles office. The fax number is provided in the Study Reference Manual.

11.2.5. Reporting Pregnancy and Coordination With the Pregnancy Registry

Throughout the study, female patients of childbearing potential should be asked about their pregnancy status and possible pregnancies/spontaneous abortions since their last consultation with their neurologist.

If female patients become pregnant at any time during the Fampyra observational study period, the Investigator or site staff must report the pregnancy to Quintiles as soon as possible and provide follow-up report(s) of pregnancy outcomes.

A Fampyra pregnancy registry is being conducted independently of the Fampyra observational study, and all pregnant women taking Fampyra (regardless of participation in any studies) will be offered participation in the Fampyra pregnancy registry. Pregnant women may be dually enrolled into Fampyra observational study and the pregnancy registry.

Please note that congenital abnormalities/birth defects in the offspring of male or female patients should be reported as an SAE if conception occurred during the Fampyra treatment period.

CONFIDENTIAL

The information contained herein may not be used, disclosed, or published without the written consent of Biogen Idec MA Inc.

11.3. Classification of Events

11.3.1. Relationship of Events to Fampyra Treatment

The following definitions should be considered when evaluating the relationship of AEs and SAEs to the Fampyra treatment:

Relationship of Event to Fampyra Treatment	
Not related	An AE will be considered “not related” to the use of Fampyra if there is not a possibility that the event has been caused by Fampyra. Factors pointing toward this assessment include, but are not limited to, the lack of reasonable temporal relationship between administration of the drug and the event, the presence of a biologically implausible relationship between the product and the AE (e.g., the event occurred before administration of the drug), or the presence of a more likely alternative explanation for the AE.
Related	An AE will be considered “related” to the use of Fampyra if there is a possibility that the event may have been caused by Fampyra. Factors that point toward this assessment include, but are not limited to, a positive rechallenge, a reasonable temporal sequence between administration of the drug and the event, a known response pattern of the suspected drug, improvement following discontinuation or dose reduction, a biologically plausible relationship between the drug and the AE, or a lack of an alternative explanation for the AE.

CONFIDENTIAL

The information contained herein may not be used, disclosed, or published without the written consent of Biogen Idec MA Inc.

12. STATISTICAL METHODS AND DETERMINATION OF SAMPLE SIZE

12.1. Statistical Analysis Plan

Statistical analyses will be exploratory and descriptive in nature. Details of the analyses to be carried out will be included in the statistical analysis plan.

12.2. Patient Population

All patients who are enrolled into the study and receive at least 1 dose of Fampyra will be included in the safety population and used for all analyses.

12.3. Baseline Patient Characteristics

Descriptive statistics (i.e., mean, standard deviation, median, minimum, and maximum) will be provided for continuous variables. Counts and percentages will be provided for categorical variables.

12.4. Safety Analysis

Safety information recorded will be coded using the most recent version of the Medical Dictionary for Regulatory Activities available at the time of study start.

Safety data will be analyzed to detect any potential new and unexpected safety signals and to further evaluate any AEs of particular interest (Section 11.2.2). All safety summaries will be presented for the safety population.

The number and percentage of patients with SAEs, AEs leading to Fampyra dosage change or discontinuation, and other reported events will be presented by System Organ Class and Preferred Term along with the relationship to Fampyra. The incidence of AEs experienced by the patient at the time of Fampyra overdose and AEs of particular interest will also be summarized by System Organ Class and Preferred Term.

The incidence of SAEs and other events will be summarized for the safety population by age group (≥ 65 years and < 65 years) and compared to published data and other sources.

In addition, the rates (number of events per person-year of exposure) of AEs leading to discontinuation of Fampyra, SAEs, and AEs of particular interest (e.g., seizures) will be calculated.

Drug Utilization

The pattern of Fampyra use (dose and duration) will be summarized descriptively. The underlying disease subtype, dosage change, or discontinuation will also be summarized. Additionally, dosing deviations from the local Fampyra label, PI, or prescription information (including incidence of overdoses) will be summarized.

CONFIDENTIAL

The information contained herein may not be used, disclosed, or published without the written consent of Biogen Idec MA Inc.

Risk Minimization

The number and percentage of patients with a neurological assessment of walking within 14 days after the start of dosing with Fampyra will be presented to assess whether appropriate follow-up of effectiveness was performed.

Adherence to contraindications will be assessed by review and summaries of data (i.e., medical history, creatinine clearance at baseline and concomitant medications). Summaries of AEs of particular interest will also be summarized by whether there was a relevant contraindication.

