All patients who are enrolled in the study and receive at least 1 dose of Fampyra will be included in the safety population. All analyses will be presented for the safety population.

Baseline Patient Characteristics

Descriptive statistics (i.e., mean, standard deviation, median, minimum, and maximum) will be provided for continuous variables. Counts and percentages will be provided for categorical variables.

CONFIDENTIAL

The information contained herein may not be used, disclosed, or published without the written consent of Biogen Idec MA Inc.

Safety Analysis

Safety data will be coded using the current version of the Medical Dictionary for Regulatory Activities available at the time of study start.

Safety data will be analyzed to detect any potential new and unexpected safety signals and to further evaluate AEs of particular interest. All safety summaries will be presented for the safety population.

The number and percentage of patients with SAEs, AEs leading to Fampyra dosage change or discontinuation, and other reported events will be presented by System Organ Class and Preferred Term along with the relationship to Fampyra.

The incidence of SAEs and other events will be summarized for the safety population by age group (≥ 65 years and < 65 years) and compared to published data and other sources.

In addition, the rates (number of events per patient-year of exposure) of AEs leading to discontinuation of Fampyra and SAEs (including seizures) will be calculated.

Drug Utilization

The pattern of Fampyra use (dose and duration) will be summarized descriptively. The underlying disease subtype, dosage change, or discontinuation will also be summarized. Additionally, dosing deviations from the local Fampyra label, PI, or prescription information (including incidence of overdoses) will be summarized.

Risk Minimization

The number and percentage of patients with a neurological assessment of walking within 14 days after the start of dosing with Fampyra will be presented to assess whether appropriate follow-up of effectiveness was performed.

Adherence to contraindications will be assessed by review and summaries of data (i.e., medical history, creatinine clearance at baseline, and concomitant medications). Summaries of AEs of particular interest will also be summarized by whether there was a relevant contraindication.

Other Observational Points

Summary statistics at each timepoint, as well as changes

CONFIDENTIAL

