4. SCHEDULES OF ASSESSMENTS FOR OBSERVATIONAL STUDY 218MS401

4.1. INVESTIGATOR SCHEDULE OF ASSESSMENTS FOR OBSERVATIONAL STUDY 218MS401

Assessments ^a	Visit	Enrollment	Follow-Up ^b	
		Baseline ^c	Baseline Until Month 12 Study Completion	Early Treatment/Study Discontinuation ^d
Informed consent		✓		
Assess eligibility		✓		
Demographics		✓		
Creatinine clearance (if serum creatinine is available)		✓	✓	✓
Urine culture (if available)		✓	✓	✓
Review medical history		✓		
EDSS assessment		✓		
Previous (past 6 months) and current treatment (if any) for underlying MS disease		✓		
Continuous concomitant procedures and medications		✓	✓	✓
Fampyra treatment (start and stop date, dose, indication, and reason for use) ^e		✓ ^d	✓	✓
Safety (SAEs, AEs leading to Fampyra dosage change or discontinuation, AEs experienced by the patient at the time of Fampyra overdose, instances of overdose, and AEs of particular interest)			✓	✓
Neurological assessment of walking			✓ ^f	
Physician's CGI-I of walking ability			✓ ^g	✓

- a. Refer to Section 10 for details of study procedures.
- b. Sites can collect data at any timepoint between Baseline and Month 12 either by telephone contact (except for the assessment of CGI-I) or during routine local clinical practice site visits.
- c. Baseline assessments must occur prior to the first dose of Fampyra.
- d. Patient can continue on study even after terminating treatment. If a patient is discontinued from the study, then both the End of Treatment and End of Study case report forms (CRFs) should be completed. If the patient discontinued treatment early, but continued in the study, then the End of Treatment CRF should be completed as soon as possible after terminating treatment, and the End of Study CRF should be completed at the conclusion of the study.
- e. Information on previous exposure to any formulations of fampridine (i.e., 4-AP) prior to Enrollment/Baseline should be recorded.
- f. At intervals indicated by local marketing authorization and clinical practice.
- g. If decline in walking ability is observed, physicians should consider an interruption to treatment in order to reassess the benefits of Fampyra. The re-evaluation should include withdrawal of Fampyra and performing the walking test. Fampyra should be discontinued if patients no longer receive walking benefit.

CONFIDENTIAL

The information contained herein may not be used, disclosed, or published without the written consent of Biogen Idec MA Inc.

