9.3. Concomitant Therapies and Procedures

In addition to Fampyra, any other treatments or procedures that are considered necessary for the patient's welfare may be given at the discretion of the Investigator. Administration of continuous concomitant procedures and medications (including herbals and nutraceuticals) must be reported in the appropriate section of the CRF along with reasons for use. Continuous concomitant procedures and medications are defined as a treatment administered regularly for 2 weeks or more. The generic names for concomitant medications should be recorded, if possible. The total daily dose should be recorded in the CRF whenever possible.

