10.1. Enrollment (Baseline)

The Investigator will collect the following data at the Enrollment Visit (Baseline):

- assessment of eligibility for the Fampyra observational study
- informed consent for participating in the Fampyra observational study
- demographic data
- record creatinine clearance if serum creatinine is already available per normal practice (not specifically performed for the study)
- obtain urine culture (if available)
- medical history (in reference to the time prior to enrollment): assessment of clinically significant medical and surgical history and concomitant diseases (collected according to body system codes); known cardiovascular risk factors: the presence or absence of specific cardiovascular risk factors (e.g., conduction disorder, left-ventricular hypertrophy, coronary heart disease, hypertension, alcohol abuse, stress, smoking); MS disease classification
- assessment and recording of EDSS [Kurtzke 1983]
- previous (past 6 months) and current treatment (if any) for the underlying MS disease: use and duration including, but not limited to, disease-modifying, antineoplastic, or other immunosuppressive medications and systemic steroids
- continuous concomitant procedures and medications, including herbal preparations and nutraceuticals (defined as a treatment used regularly for ≥ 2 weeks)
- Fampyra treatment: dose, indication, reason for use, and start date (if started on the day of enrollment, otherwise record start date at the next visit). Information on previous exposure to any formulations of fampridine prior to Enrollment should be recorded.
- patient assessment of physical and psychological impact of MS using MSIS-29

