10.2. Postenrollment Follow-Up

Data will be collected during the Follow-Up period: approximately 1 year after Enrollment. Follow-Up visits should occur according to clinical practice, with data collection possible at any timepoint during this period, either by telephone contact (except CGI-I) or during routine local clinical practice site visits. The following data will be collected during this period:

CONFIDENTIAL

The information contained herein may not be used, disclosed, or published without the written consent of Biogen Idec MA Inc.

- record creatinine clearance if serum creatinine is already available per normal practice (not specifically performed for the study)
- obtain urine culture (if available)
- status of treatment with Fampyra: dose, start and stop date (if applicable), and date of dosage change or interruption, or date of discontinuation
- changes in continuous concomitant therapies
- SAEs, AEs leading to Fampyra dosage change or discontinuation, AEs experienced by the patient at the time of Fampyra overdose, instances of overdose, and AEs of particular interest (see Section 11.2.2)
- Physician's CGI-I of walking ability (needs to be assessed during clinical visit, not by telephone)

A neurological assessment of walking may be conducted, in line with the SmPC or other local prescribing information.

Additionally, MS patients will be asked to complete assessments of physical and psychological impact of MS using MSIS-29.

Throughout the study, female patients of childbearing potential should be asked about their pregnancy status and possible pregnancies/spontaneous abortions since their last consultation with their neurologist. See Section 11.2.5 for reporting pregnancies/spontaneous abortions.

Data will be collected as above for all patients, including those who are followed up after early discontinuation of Fampyra treatment (see Section 7.2).

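### Renal function and medical history enter the contraindication review only as of baseline or earlier, although creatinine clearance and events are also recorded in follow-up

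*Protocol*

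**What the plan says.** Assessing how well the risk minimization measures work is a secondary objective (Section 6.1.2). Under Risk Minimization, Section 12.4 assesses adherence to contraindications from "medical history, creatinine clearance at baseline and concomitant medications". The Synopsis has the same list with a comma after baseline: "medical history, creatinine clearance at baseline, and concomitant medications". Both places introduce the list with i.e., so it reads as complete rather than as examples. Section 12.4 then splits the AEs of particular interest by presence of a relevant contraindication.

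The data collection sections say more about timing:

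- Section 10.1 defines "medical history (in reference to the time prior to enrollment", so history ends at entry.
- Section 4.1 lists "Creatinine clearance (if serum creatinine is available" at Baseline, at Follow-Up and at Early Treatment/Study Discontinuation. Section 10.2 repeats this for follow-up: "record creatinine clearance if serum creatinine is already available per normal practice (not specifically performed for the study".
- Section 10.2 also collects "changes in continuous concomitant therapies". Section 9.3 sets the scope: "Continuous concomitant procedures and medications are defined as a treatment administered regularly for 2 weeks or more".
- Sections 11.2.1 to 11.2.3 record SAEs (all seizures among them) and AEs of particular interest from the first dose to study completion or early study discontinuation, whether or not the patient is still on Fampyra.

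**The concern.** Patients are observed for about a year, and contraindications can arise during treatment as well as be present at its start. Two of the three named inputs, renal function and diagnoses, are fixed at or before entry. The review can therefore show whether prescribing respected those contraindications at initiation, but not whether they were respected later. Eligibility (Section 8.2) already requires a prescription within the marketing authorization, so for these two inputs the review looks only at the time point that the entry criterion already addresses.

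Two outputs are affected: the adherence summary itself, and the split of AEs of particular interest. The protocol also names creatinine clearance in no other analysis, so the follow-up values are collected without a stated use. Section 5.2 expects patients aged 65 or over and patients with cardiovascular risk factors, groups in which status may change within a year.

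**Working it through.** No figure in the plan bears on this point, so the check sets the analysis rule beside the data collection.

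| Source | Window in the contraindication review (Section 12.4, Synopsis) | Window in data collection | Result |
|---|---|---|---|
| Creatinine clearance | Baseline | Baseline, follow-up, early discontinuation, if available (Sections 4.1, 10.1, 10.2) | Follow-up values not used |
| Medical history | Before enrollment, by the Section 10.1 definition | Baseline only | Later diagnoses can appear only as recorded events |
| Concomitant medications | No time limit stated | Baseline, follow-up, early discontinuation; regular use for 2 weeks or more (Sections 4.1, 9.3, 10.2) | No timing gap; shorter courses not captured |
| SAEs and AEs of particular interest | Not named as an input | First dose to study completion or early study discontinuation (Sections 11.2.1 to 11.2.3) | Not used in the review |

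**Does the baseline limit extend to medications?** No. In Section 12.4 it is attached to creatinine clearance, and the comma in the Synopsis version ("creatinine clearance at baseline, and concomitant medications") confirms that reading.

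**What happens to an emergent case?** Take a patient with no contraindication at entry whose routine creatinine at month 5 falls in a range that the local label contraindicates, and who stays on Fampyra. The month-5 value is in the database, but the review reads only the baseline value and the history before enrollment. The case does not enter the adherence measure. The AE split states no inputs or timing of its own. If it takes its contraindication status from the sentence before it, which is the only definition given, the month-5 change does not enter the split either. Any SAE or AE of particular interest in that patient is still tabulated in the general safety summaries.

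**Can the size be computed?** No. It depends on how many patients have a follow-up creatinine while on treatment, how many of those cross into a locally contraindicated range or gain a contraindicating diagnosis, and how many then continue Fampyra. The protocol gives none of these. It gives only about 5000 enrolled and an assumed 34% who drop out or discontinue treatment (Section 12.7.1).

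**The case against.** The strongest reply is that a baseline check answers a legitimate question: did prescribers respect the contraindications when they started treatment? The risk management plan, which defines the measures to be assessed, is not shown and may concern initiation only. The protocol leaves analysis details to the statistical analysis plan, and the output is secondary and descriptive. This limits the weight of the point and is a reason to keep the baseline review. It does not remove the mismatch, because the baseline limit is stated in a closed list and is not a detail left open.

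A reader might infer more than the protocol supports:

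- *That the whole review stops at entry.* It does not. Medications carry no baseline limit and are updated in follow-up, so a contraindicated long-term medicine started during the year can be detected. Risk minimization more broadly also includes the walking assessment within 14 days after the start of dosing, and dosing deviations are summarized without a baseline limit.
- *That patients with an emergent contraindication are counted as adherent, or untested patients as not contraindicated.* No such rule is written. A category for unavailable creatinine is ordinary content of a statistical analysis plan, and its absence here is not a fault.
- *That a new seizure is itself an emergent contraindication.* The protocol lists no contraindications and refers to local labels, so this cannot be assumed.
- *That the safety data are lost.* They are recorded and tabulated, on or off drug.

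Two objections bear on the remedy, and both stand. Routine creatinine testing may be prompted by illness, which would link detection of a contraindication to AEs. An event used to define a contraindication must also not be counted as an AE within the group it has just defined.

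**Conclusion.** The point holds in a limited form. For renal function and diagnoses, Section 12.4 and the Synopsis restrict the contraindication review to baseline or earlier, although the study also records creatinine clearance (where available) and the specified events during follow-up. Contraindications of these kinds that emerge on treatment therefore fall outside the adherence measure and, on the only definition given, outside the AE split.

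The size is unknown and cannot be derived from the protocol; neither can the direction or amount of any distortion in the AE split. The conclusion rests on reading the i.e. list as complete and on local labels containing renal or diagnostic contraindications that can arise within a year. It concerns one secondary descriptive summary. The primary safety tables are not affected. The change is worth making because it uses data already collected.

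**What to change.** Amend Section 12.4 (Risk Minimization) and the matching Synopsis text as follows.

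1. Keep the present review and label it as adherence at initiation of treatment.
2. Add a separate descriptive summary of contraindications, as defined by the local label, that emerge while the patient is on Fampyra. Base it on follow-up creatinine clearance, changes in continuous medications and recorded events. Report the number of patients with at least one follow-up creatinine value, and whether Fampyra was continued after the contraindication emerged.
3. For the split of AEs of particular interest, use contraindication status established before AE onset, so that an event cannot define its own group.
4. State the limits beside the results. Follow-up creatinine exists only where routinely tested, testing may be prompted by illness, and non-serious events outside the Section 11.2.2 categories are not collected. The emergent count is therefore a minimum and may be linked to AEs.

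The cost is wording in two places and some added tables and programming. No new visit, test or data item is needed.
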